### 8.2.1. Computed Tomography Scans

CT scans of the chest, abdomen, and pelvis (neck should be included, if appropriate and as clinically indicated) will be performed to assess disease at Screening and per assessment schedule in the [SoA](#). All CT scans should be performed with IV contrast and abdominal and pelvic CT scans should be performed with oral or IV contrast unless contraindicated (see Imaging Manual for details). Hybrid PET-CT scanners may be used to acquire the required CT images only if CT produced by the scanner is of diagnostic quality, adheres to specified scan parameters, and includes IV contrast (unless medically contraindicated). Non-diagnostic CT images acquired for attenuation purposes during PET-CT are NOT acceptable as the only CT scan for the time point. Diagnostic CT images with contrast (unless medically contraindicated) with a standalone CT scanner must be acquired if PET-CT is unable to acquire diagnostic CT images. If the diagnostic CT and PET are acquired on the same day, it is strongly recommended that the PET is performed prior to the CT with IV contrast as to not compromise PET results. MRI or PET/MRI can be used in place of CT if a participant cannot tolerate CT contrast agent or as clinically indicated. The same imaging modality should be used for a given participant throughout the study duration.

### **8.2.2. Positron Emission Tomography Scans**

A PET scan with FDG extending from the neck through the mid thighs will be performed to assess baseline disease at Screening and to assess disease response as per the [SoA](#); in addition to the FDG-PET imaging a diagnostic quality contrast-enhanced CT scan must be included for lesion measurements. Examinations should be consistent across all time points, including amount of tracer, location of injection, arm position, and scan delay. Note that if a participant achieves a metabolic CR, PET scans are not required at subsequent assessments. Additional PET/CT or CT or MRI examinations may be performed by the investigator in the course of the study, if deemed necessary (eg, if PD is suspected, to confirm the occurrence of a CR or to make important treatment-related decisions). If the participant discontinues from study intervention, a PET/CT scan is only required at the EOT if it was not performed in the cycle prior to the EOT. CT may be performed in lieu of PET/CT if the participant discontinues from study intervention within C1.

## **8.3. Safety Assessments**

Planned time points for all safety assessments are provided in [SoA](#). Unscheduled safety measurements may be obtained at any time during the study to assess any perceived safety issues.

### **8.3.1. Physical Examinations**

A complete PE will be performed at Screening and is to include, at a minimum, assessments of the cardiovascular, respiratory, gastrointestinal, and neurological systems. Targeted/symptom-directed PEs, including signs and symptoms of the disease under study, will be conducted at other visits as per the [SoA](#). Height will be collected at baseline and weight will be measured and recorded as per the [SoA](#).

PEs may be conducted by a physician, trained physician's assistant, or nurse practitioner as acceptable according to local regulation.

PE findings collected during the study will be considered source data and will not be required to be reported, unless otherwise noted. Any untoward PE findings that are identified during the active collection period and meet the definition of an AE or SAE ([Appendix 3](#)) must be reported according to the processes in Sections [8.4.1](#) to [8.4.3](#).

**When should it be done:**

PE is to be performed prior to infusion of study intervention.

### **8.3.2. Vital Signs**

Pre-dose vital signs will be reported on the CRF. All other vital signs collected during the course of the study will be considered source data only and will not be required to be reported on the CRF.

Any untoward vital sign findings that are identified during the active collection period and meet the definition of an AE or SAE ([Appendix 3](#)) must be reported according to the processes in Section [8.4.1](#) to [Section 8.4.3](#).

#### **8.3.2.1. Blood Pressure and Pulse Rate**

BP and PR measurements will be assessed per institutional standards with a completely automated device. Manual techniques will be used only if an automated device is not available.

Vital signs will be taken before blood collection for laboratory tests.

In case of logistical issue, the vitals can be taken after blood collection for laboratory tests after the participant has rested as per standard of care.

Vital signs consist of a single measurement of PR and single BP measurement.

#### **8.3.2.2. Temperature and Respiratory Rate**

Temperature and respiratory rate findings collected during the study will be considered source data and will not be required to be reported, unless associated with an AE/SAE or otherwise noted.

#### **8.3.3. Electrocardiograms**

Standard 12-lead ECGs utilizing limb leads (with a 10-second rhythm strip) should be collected at times specified in the [SoA](#) section of this protocol using an ECG machine that automatically calculates the heart rate and measures PR interval, QT interval, QTcF, and QRS complex. For ECG machines that do not report QTcF, calculation of QTcF from QT and heart rate, for example using online tools, is required. Alternative lead placement methodology using torso leads (eg, Mason-Likar) should not be used given the potential risk of discrepancies with ECGs acquired using standard limb lead placement. All scheduled ECGs should be performed after the participant has rested quietly for at least 5 minutes in a supine position.

If a) a post-dose QTcF interval remains  $\geq 60$  ms from the baseline and is  $> 450$  ms; or b) an absolute QT value is  $\geq 500$  ms for any scheduled ECG for greater than 4 hours (or sooner, at the discretion of the investigator); or c) QTcF intervals get progressively longer, the participant should undergo continuous ECG monitoring.

A cardiologist should be consulted if QTcF values do not return to less than the criteria listed above after 8 hours of monitoring (or sooner, at the discretion of the investigator).

In some cases, it may be appropriate to repeat abnormal ECGs to rule out improper lead placement as contributing to the ECG abnormality. It is important that leads be placed in the same positions each time in order to achieve precise ECG recordings. If a machine-read QTcF value is prolonged, as defined above, repeat measurements may not be necessary if a

qualified medical provider's interpretation determines that the QTcF values are in the acceptable range.

ECG values of potential clinical concern are listed in [Appendix 8](#).

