**Table 1. Study Schedule of Assessment**

Visit Identifier	Screen	On-Treatment Period (28-day Cycle)												Notes			
		Cycle 1				Cycle 2-3				≥Cycle 4				EOT	FU visits		LTFU
Cycle Day	≤28d	D1	D4	D8	D15	D22	D1	D8	D15	D22	D1	D15	7d	28d	90d	Q12W	
 
Day relative to start of study intervention (Day 1).
 

Visit Window		(±1d)	(±2d)	(±2d)	(±2d)	(±2d)	(±2d)	(±2d)	(±2d)	(±2d)	(±2d)	(±2d)	(±2d post-last TX)	(28-35d post-last TX)	(+7 post-last TX)	(±14d post 90d FU)	
 
After 1 year of study intervention, cycle visit date windows are ±7d.
 

Vital signs	X	X	X	X	X	X	X	X	X	X	X	X	X	X			
 
On days of infusion: as per local guidelines for monoclonal antibodies, with a minimum as follows for each infusion of PF-07901801 and tafasitamab.           
 
PF-07901801: C1D1: pre (within 15 min prior), EOI (±15 min), (end of): 2h (±15 min). ≥C1D8: pre and EOI (±15 min).
 
Tafasitamab: pre, 15 (±5), 30 (±10), and then every 60 (±15) minutes during infusion and at EOI (± 20 min). After 3 infusions: pre and EOI (±15 min).
 
 
 
See Section 8.3.2 for additional information.
 

12-Lead ECG	X	X					X			X		X	X				
 
C1D1, C2D1, C3D1: Pre-PF-07901801 dose, PF-07901801 EOI (window for EOI: +30 min).
 
C4D1, C5D1, C6D1: pre PF-07901801 dose
 
See Section 8.3.3 for additional information.
 

B-symptoms	X	X					X			X		X					
 
See Section 8.3.6.
 

ECOG assessment	X																
 
Per Appendix 13.
 

PFIZER CONFIDENTIAL

CT02-GSOP Oncology Clinical Protocol Template (01 April 2022)

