**Medical Conditions:**

1. Prior treatment with anti-CD47 or anti-CD19 (other than CAR-T) or immunomodulatory agents like thalidomide or lenalidomide.
2. Primary refractory DLBCL:
  - Primary refractory definition for this protocol: response less than a PR to first-line therapy or progression during or within 6 months after completion of first line of therapy.
3. High-grade lymphoma (formerly known as 'double' or 'triple hit' DLBCL) or CNS lymphoma (primary or secondary).
  - Simultaneous detection of MYC with BCL2 and/or BCL6 translocation(s) defined by fluorescence in situ hybridization. MYC, BCL2, BCL6 testing prior to study enrollment is not required. FISH testing is required prior to enrollment if historical results are not available.
  - CNS lymphoma involvement – present or past medical history
4. Any history of malignancies other than DLBCL except for:
  - Basal cell or squamous cell carcinoma of the skin or Bowen's disease that has adequately been treated.
  - Any prior malignancies  $\geq 3$  years before randomization with no subsequent evidence of recurrence or progression without treatment regardless of stage of disease.

- Any prior malignancies in situ, stage 0 – 1 cancer <3 years before randomization that has a remote probability of recurrence or progression per investigator.
- 5. Prior cancer treatment, radiotherapy within 2 weeks or major surgery within 2 weeks.
- 6. Prior allogeneic stem cell transplantation; autologous stem cell transplantation within 12 weeks prior to enrollment.
- 7. Significant cardiac/cardiovascular/thromboembolic disease, such as
  - Symptomatic congestive heart failure (New York Heart Association Class III or IV), symptomatic coronary artery disease, myocardial infarction, unstable angina within the last 6 months or known LVEF <40% (as determined by a MUGA scan or Echo)
  - Prolonged QTcF interval >470 msec at screening.
  - History of symptomatic ventricular or supraventricular arrhythmia (intermittent or permanent atrial fibrillation is not an exclusion criterion), inherited arrhythmia, or bradycardia
  - History of deep venous thrombosis or pulmonary embolism. Known, acquired, or hereditary thrombophilia.
- 8. Participants with active, uncontrolled bacterial, fungal, or viral infection, including (but not limited to) COVID-19/SARS-CoV-2, HBV, HCV, or AIDS related illness.

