##### Safety QTcF Assessment

Degree of Prolongation	Mild (ms)	Moderate (ms)	Severe (ms)
Absolute value	>450-480	>480-500	>500
Increase from baseline		30-60	>60

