## 10.8. Appendix 8: ECG Findings of Potential Clinical Concern

ECG Findings That May Qualify as AEs

Marked sinus bradycardia (rate <40 bpm) lasting minutes.

New PR interval prolongation >280 ms.

New prolongation of QTcF to >480 ms (absolute) or by <math>\geq</math>60 ms from baseline.

New-onset atrial flutter or fibrillation, with controlled ventricular response rate: ie, rate <120 bpm.

New-onset type I second degree (Wenckebach) AV block of >30 seconds' duration.

Frequent PVCs, triplets, or short intervals (<30 seconds) of consecutive ventricular complexes.

ECG Findings That May Qualify as SAEs

QTcF prolongation >500 ms.

New STT changes suggestive of myocardial ischemia.

New onset LBBB (QRS complex >120 ms).

New-onset right bundle branch block (QRS complex >120 ms).

Symptomatic bradycardia.

Asystole:

In awake, symptom-free participants in sinus rhythm, with documented periods of asystole <math>\geq</math>3.0 seconds or any escape rate <40 bpm, or with an escape rhythm that is below the AV node.

In awake, symptom-free participants with atrial fibrillation and bradycardia with 1 or more pauses of at least 5 seconds or longer.

Atrial flutter or fibrillation, with rapid ventricular response rate: rapid = rate >120 bpm.

Sustained supraventricular tachycardia (rate >120 bpm) ("sustained" = short duration with relevant symptoms or lasting >1 minute).

Ventricular rhythms >30 seconds' duration, including idioventricular rhythm (heart rate <40 bpm), accelerated idioventricular rhythm (HR >40 bpm to <100 bpm), and

monomorphic/polymorphic ventricular tachycardia (HR >100 bpm [such as torsades de pointes]).

- Type II second degree (Mobitz II) AV block.
- Complete (third degree) heart block.

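### The 500 ms trigger for continuous ECG monitoring is set on uncorrected QT, so some sustained QTcF values above 500 ms meet neither numeric limb of the rule

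*Protocol*

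**What the plan says.** Protocol 8.3.3 sends a participant to continuous ECG monitoring under any of three limbs:

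- (a) post-dose QTcF stays at least 60 ms above baseline and is above 450 ms;
- (b) "or b) an absolute QT value is" at least 500 "ms for any scheduled ECG for greater than 4 hours (or sooner, at the discretion of the investigator");
- (c) QTcF keeps lengthening, with no threshold given.

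The same section lists QT and QTcF as separate measurements and makes QTcF available for every tracing: "For ECG machines that do not report QTcF, calculation of QTcF from QT and heart rate, for example using online tools, is required". Its follow-on rule is written in QTcF: "A cardiologist should be consulted if QTcF values do not return to less than the criteria listed above after 8 hours of monitoring".

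Elsewhere the protocol also sets its limits on QTcF:

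- Section 5.2, exclusion criterion 7: "Prolonged QTcF interval >470 msec at screening".
- Section 9.4.5.1: the table headed "Safety QTcF Assessment" bands an absolute value above 500 ms as severe.
- Appendix 8: "QTcF prolongation >500 ms" is a finding that may qualify as an SAE.

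SAP 6.7.6 tabulates QT and QTc together at 500 ms, so uncorrected QT is a tracked measure as well.

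**The concern.** Uncorrected QT shortens as heart rate rises, so a QT limit of 500 ms becomes harder to reach above 60 bpm for the same QTcF. No limb of 8.3.3 carries an absolute QTcF limit of 500 ms. If limb (a) does not cover every QTcF above 500 ms, the rule gives no numeric instruction to monitor at a level the protocol itself calls severe.

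The cardiology consult is affected too. It compares QTcF with the listed criteria after 8 hours of monitoring, but limb (b) supplies no QTcF value for that comparison. A participant who never meets a monitoring limb never reaches the consult step.

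**Working it through.** The plan states no figure on this point, so the check is to apply limbs (a) and (b) as written.

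**Inputs**

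- Limb (a): rise of at least 60 ms and QTcF above 450 ms (Protocol 8.3.3).
- Limb (b): QT of at least 500 ms, sustained (Protocol 8.3.3).
- Highest QTcF allowed at screening: 470 ms (Protocol 5.2, exclusion criterion 7).
- Fridericia correction: QTcF = QT / RR^(1/3), with RR = 60/HR (SAP 6.7.6).
- Heart rate: an assumption, shown as a range, because the documents give no distribution.

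**Step 1: where limb (a) fails.** For a QTcF above 500 ms the 450 ms condition is always met, so (a) is missed only when QTcF − baseline < 60. With baseline at or below 440 ms, any QTcF above 500 is a rise of more than 60, so (a) always applies. With baseline above 440 ms, a QTcF above 500 and below baseline + 60 misses (a). In whole milliseconds:

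| Baseline QTcF (ms) | QTcF above 500 that misses (a) | Count |
|---|---|---|
| 440 | none | 0 |
| 442 | 501 | 1 |
| 450 | 501–509 | 9 |
| 460 | 501–519 | 19 |
| 470 | 501–529 | 29 |

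Over baselines 441 to 470 the counts run 0, 1, 2, …, 29, and their sum is 29 × 30 / 2 = 435 baseline/post-dose pairs.

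**Step 2: where limb (b) also fails.** Rearranging Fridericia, QT = QTcF × (60/HR)^(1/3). QT is below 500 when HR > 60 × (QTcF/500)^3.

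| QTcF (ms) | HR above which QT < 500 (bpm) | QT at 75 bpm (ms) |
|---|---|---|
| 501 | 60.4 | 465.1 |
| 510 | 63.7 | 473.4 |
| 515 | 65.6 | 478.1 |
| 520 | 67.5 | 482.7 |
| 529 | 71.1 | 491.1 |

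The largest threshold is 71.1 bpm, so at 72 bpm or more all 435 pairs miss (b) as well, however long the value lasts. At 60 bpm or below, QTcF above 500 implies QT above 500, and (b) applies if the value is sustained.

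**Step 3: worked case.** Baseline 460, post-dose 515, heart rate 75. The rise is 515 − 460 = 55 ms, below 60, so (a) is not met. QT = 515 × (60/75)^(1/3) = 478.1 ms, below 500, so (b) is not met.

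**Step 4: alternatives for limb (b).** If (b) reads QT or QTcF of at least 500 ms, none of the 435 pairs escapes once the 4-hour condition holds. Replacing QT outright by QTcF would also close the gap but would drop some cases that now trigger. A QT of 500 corresponds to a QTcF of 470.5 at 50 bpm and 485.7 at 55 bpm. Keeping both measures retains these.

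**The case against.** The best counter-argument is that QTcF was meant in (b). The consult sentence compares QTcF with the listed criteria, a later sentence on repeat readings treats those criteria as defining a prolonged QTcF, and the word absolute may only contrast with the change from baseline in (a). That may be the intent. But the section lists QT and QTcF as separate measurements, so a site that follows the text will apply QT.

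The other points reduce the effect and stand to that extent:

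- **Limb (c).** Every pair in the gap is at least 31 ms above baseline (470 to 501). If the rise builds over successive ECGs, (c) applies at any heart rate. It does not clearly cover an abrupt rise that then holds steady.
- **Persistence.** The Schedule of Activities has "C1D1, C2D1, C3D1: Pre-PF-07901801 dose, PF-07901801 EOI (window for EOI: +30 min"), and pre-dose ECGs only on C4D1 to C6D1. Scheduled tracings will not show more than 4 hours' persistence, so even a corrected (b) needs repeat ECGs or the existing discretion wording. That discretion shortens the 4 hours; it does not change which interval is measured.
- **Other safeguards.** Appendix 8 recommends alerts for its listed findings, and section 9.4.5 has the sponsor reviewing ECGs throughout. Neither directs continuous monitoring or a consult. The severe band in 9.4.5.1 is an analysis category.
- **Scale.** The 435 pairs are grid points, neither participants nor a probability. The risk table in section 2.3.1 names no QT risk. Phase 1b was planned for about 20 participants, and Phase 2 will not start. Section 10.1.10 does allow treatment and safety assessments to continue after a termination unrelated to safety, so 8.3.3 may still apply to someone.

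**Conclusion.** The concern holds. As written, a sustained QTcF above 500 ms from a baseline above 440 and up to 470 ms, with a rise under 60 ms, misses limb (a). It also misses limb (b) once heart rate exceeds about 60 to 71 bpm, depending on QTcF. In that region 8.3.3 has no numeric trigger for monitoring, or for the consult that follows it, and relies on limb (c) or on judgement.

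The result rests on the Fridericia formula in SAP 6.7.6 and on reading QT in (b) literally. The 470 ms bound is a screening limit. SAP 3.4 takes the last assessment before treatment as the safety baseline, so a baseline above 470 ms is possible and the gap could extend further. Without a distribution of heart rate or baseline QTcF, the number of participants affected cannot be estimated. No endpoint, DLT rule or planned analysis changes. This is a correction that should be made to a participant-safety rule, with limited practical consequence in a study that is closing.

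**What to change.** In Protocol 8.3.3(b), change *an absolute QT value* to *an absolute QT or QTcF value*. Keep the 500 ms threshold, the 4-hour condition and the discretion wording. This also gives the consult rule a QTcF limit to refer back to.

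The cost is two added words, made as a protocol edit or clarified to sites. No new measurement is needed. The only burden is that a few more participants may be monitored. The change does not make a single reading a trigger: persistence still has to be shown by repeat ECGs or judged by the investigator.

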**When should it be done:**

ECG assessments should precede blood collection for clinical laboratory tests. In case of logistical issue, ECG can be performed after blood collection for clinical laboratory tests after the participant has rested quietly for at least 5 minutes in a supine position.

#### **8.3.4. Clinical Safety Laboratory Assessments**

See [Appendix 2](#) for the list of clinical safety laboratory tests to be performed and the [SoA](#) for the timing and frequency. All protocol-required laboratory assessments, as defined in [Appendix 2](#), must be conducted in accordance with the Laboratory Manual and the [SoA](#). Unscheduled clinical laboratory measurements may be obtained at any time during the study to assess any perceived safety issues and results recorded in the CRF.

The investigator must review the laboratory report prior to the infusions, document this review, and record any clinically significant changes occurring during the study in the AE section of the CRF. Clinically significant abnormal laboratory test findings are those that are not associated with the underlying disease, unless judged by the investigator to be more severe than expected for the participant's condition.

All laboratory tests with values considered clinically significant and abnormal during participation in the study or within 28 calendar days after the last administration of PF-07901801 and/or lenalidomide or 90 days after the last administration of tafasitamab should be repeated until the values return to normal or baseline or are no longer considered clinically significant by the investigator or study medical monitor.

If such values do not return to normal/baseline within a period of time judged reasonable by the investigator, the etiology should be identified and the sponsor notified.

See [Appendix 6](#) for suggested actions and follow-up assessments in the event of potential DILI.

See [Appendix 7](#) for instructions for laboratory testing to monitor kidney function and reporting laboratory test abnormalities.

Screening laboratories may be used as pre-dose baseline if they are within 3 days of C1D1, and therefore there is no need to repeat clinical laboratory assessments on C1D1 in this case. If laboratory values are not within eligibility, blood test may be repeated once.

All safety laboratory results must be available prior to dosing to determine if dose modifications are necessary, may be drawn up to 72 hours prior to dosing visit date.

